9.0 Privacy/Confidentiality Issues

Data will be entered by authorized study personnel only into RedCap, which is a password protected and access restricted research data entry system.

All study visits will take place in a private room. Informed consent will be obtained only after the study is thoroughly explained to the prospective subject and all his questions have been answered.

10.0 Follow-up and Record Retention

The study will last approximately three years. Data will be stored in RedCap in accordance with NIH and Indiana University Guidelines or until such time as the records are no longer needed.

Vitamin E for NASH Treatment in HIV Infected Individuals

Principal Investigator

[name]
Indiana University School of Medicine
Department of Medicine
Division of Gastroenterology/Hepatology
[name]
[name]

Statistical Plan

NCT number: 03669133

Date of Document: September 20, 2020

Statistical Considerations

Because host genetic factors contribute to the response to therapy, pre-therapy baseline liver expression profiles will be studied to identify expression signature that predict response to vitamin E therapy. This approach has been used in other liver disease such as hepatitis C. For example, in one study, pre-treatment peripheral blood monocytes gene expression signature predicted response to hepatitis C therapy with 94% accuracy (143).

Quantitative global gene expression analysis on fresh frozen liver tissue from subjects participating in the clinical trial will be performed. Based on prior experience, it is expected to have a portion of the liver biopsy snap frozen and available for expression analysis on a sizable proportion of the subjects (>50%) undergoing liver biopsies as part of Specific Aim 2 who are the primary source for the proposed clinical trial. As such, HumanHT-12 v4 Expression BeadChip will be used for this aim. This chip provides genome-wide transcriptional coverage of well-characterized genes and their splice variants, and targets more than 47,000 probes derived from the NCBI RefSeq Release 38 (November 7, 2009) and other sources.

After detectable transcripts are identified, expression data will be standardized. The t- test statistic will be utilized to measure the expression difference between the sample means (responders vs. non-responders) in units of the standard deviation for which the difference can be tested using certain p value. For this, a significance cut-point of $p < 0.001$ will be used. Then hierarchical clustering and gene network and pathway analysis will be performed to identify those predicting response to vitamin E therapy. A logistic multivariate-based analysis will be used to build up a receiver operating characteristic (ROC) curve, and the area under the ROC curve (AUC) will be calculated to assess the average sensitivity of the biomarker in discriminating the responders and non-responders.

All endpoints are measured as the change from baseline to 24 weeks. The primary outcome measure is the change in hepatic fat content as measured by central reading of MR-PDFF performed at baseline and end of study. Secondary endpoints will be changes in inflammatory markers (liver enzymes, TNF-alpha, IL-10 levels), serum K-18, Liver stiffness and CAP measurement by TE, and MDA level as a marker of oxidative stress.

The primary outcome is the improvement in liver fat as assessed by MR-PDFF at end of treatment compared to baseline. To our knowledge, there are no data on studying the effect of vitamin E on MR-PDFF in NASH patients with HIV. Using an alpha of 5% and a two-sample independent t-test and equal variance assumption, a sample size of 25 per group will have 91% power to detect an effect size of 0.97 and will have 80% power to detect an effect size as small as 0.81. To ensure this number is achieved, 28 subjects per group will be recruited, allowing for 10% drop-out during the trial. The primary purpose of this pilot study is to generate preliminary data to estimate the mean and variability of improvement in liver fat with vitamin E in HIV infected patients with NASH.

Primary outcomes analysis: The primary analysis will be based on an analysis of covariance (ANCOVA) to compare the improvement in liver fat due to vitamin E relative to placebo. The model will include one dummy variable for treatment group indicator as well as baseline demographic characteristics and baseline liver fat. The 95% confidence intervals for the difference between the two treatment groups will be reported.

Secondary outcomes analysis: Secondary efficacy end points are continuous and as such the ANCOVA model will be used as described for analyzing the primary outcome except that the model will include the baseline value of the response variable.

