2.0 Rationale and Specific Aims

The aim of this study is to conduct a proof-of-concept clinical trial to evaluate the efficacy of vitamin E for treatment of NASH in HIV infected individuals.

This project is a proof-of-concept, randomized controlled trial to test the hypothesis that vitamin E improves hepatic steatosis and markers of hepatic necroinflammation in HIV infected individuals with biopsy-proven NASH. In this placebo-controlled, double-blind, randomized pilot clinical trial we will randomize 56 eligible participants at two different sites to receive 800 IU/daily of vitamin E or matching placebo for 6 months. The primary endpoint is the change in hepatic fat content from baseline to end of treatment in the two groups. Subjects will undergo MR imaging to measure hepatic fat content using MR-PDFF at baseline and at the end of treatment. In the randomization visit, all participants will receive standard recommendations about lifestyle modifications including healthy

Vitamin E for NASH Treatment in HIV Infected Individuals

dieting, exercise, and weight loss, and use of alcohol and dietary and herbal supplements.

Vitamin E is a well-established therapy for NASH in the non-HIV population (see section B.5 in Significance). While variable dosages ranging from 100-1200 IU/daily have been used with reported beneficial effects on liver enzymes and histology, including steatosis, the dose chosen in this trial is the same used in PIVENS, the largest randomized clinical trial establishing the efficacy of vitamin E (90) and is the dose recommended by the multi-society guidelines for treatment of NASH in the non-HIV population (75). As vitamin E effects on ALT could be seen in as early as 4 weeks (92) and on histology in 6 months (87, 88), we believe the 6 month duration of the proposed proof-of-principle study is rational. Further, there is emerging data to suggest low vitamin E level may be seen in a small subset (7%) of HIV infected men (95) and in association with use of certain ART (96). Benefits reported with vitamin E use in the HIV infected patient in earlier small studies include reduction in oxidative stress and HIV viral load and increased viability of circulating lymphocytes with (97, 98). Finally, vitamin E is relatively inexpensive and has no interactions with any ART drugs. Thus, there is a strong rationale to investigate vitamin E as a therapy for NASH in the HIV infected individuals.

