8.0 Statistical Considerations

Because host genetic factors contribute to the response to therapy, pre-therapy baseline liver expression profiles will be studied to identify expression signature that predict response to vitamin E therapy. This approach has been used in other liver disease such as hepatitis C. For example, in one study, pre-treatment peripheral blood monocytes gene expression signature predicted response to hepatitis C therapy with 94% accuracy (143).

Quantitative global gene expression analysis on fresh frozen liver tissue from subjects participating in the clinical trial will be performed. Based on prior experience, it is expected to have a portion of the liver biopsy snap frozen and available for expression analysis on a sizable proportion of the subjects (>50%) undergoing liver biopsies as part of Specific Aim 2 who are the primary source for the proposed clinical trial. As such, HumanHT-12 v4 Expression BeadChip will be used for this aim. This chip provides genome-wide transcriptional coverage of well-characterized genes and their splice variants, and targets more than 47,000 probes derived from the NCBI RefSeq Release 38 (November 7, 2009) and other sources.

After detectable transcripts are identified, expression data will be standardized. The t-test statistic will be utilized to measure the expression difference between the sample means (responders vs. non-responders) in units of the standard deviation for which the difference can be tested using certain p value. For this, a significance cut-point of $p < 0.001$ will be used. Then hierarchical clustering and gene network and pathway analysis will be performed to identify those predicting response to vitamin E therapy. A logistic multivariate-based analysis will be used to build up a receiver operating characteristic (ROC) curve, and the area under the ROC curve (AUC) will be calculated to assess the average sensitivity of the biomarker in discriminating the responders and non-responders.

All endpoints are measured as the change from baseline to 24 weeks. The primary outcome measure is the change in hepatic fat content as measured by central reading of MR-PDFF performed at baseline and end of study. Secondary endpoints will be changes in inflammatory markers (liver enzymes, TNF-alpha, IL-10 levels), serum K-18, Liver stiffness and CAP measurement by TE, and MDA level as a marker of oxidative stress.

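### The gene-expression analysis is meant to predict response to vitamin E, but it includes no placebo contrast or expression-by-treatment interaction, so it cannot tell a vitamin E-specific marker from a prognostic one

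*SAP*

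**What the plan says.** Protocol 8.0 and the SAP carry the same text. The aim is specific to the treatment: "pre-therapy baseline liver expression profiles will be studied to identify expression signature that predict response to vitamin E therapy". On the material, the SAP says "Quantitative global gene expression analysis on fresh frozen liver tissue from subjects participating in the clinical trial will be performed". It expects frozen tissue from more than half of the subjects biopsied under Specific Aim 2, who are the main source of trial participants.

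The method has three steps.
- A t-test per transcript at p < 0.001, used to "measure the expression difference between the sample means (responders vs. non-responders", on a chip that "targets more than 47,000 probes derived from the NCBI RefSeq Release 38".
- After that, "hierarchical clustering and gene network and pathway analysis will be performed to identify those predicting response to vitamin E therapy".
- A logistic model with an ROC curve, to "assess the average sensitivity of the biomarker in discriminating the responders and non-responders".

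None of these steps names the treatment arm, a comparison with placebo or an interaction. Responder is not defined. The only vitamin E versus placebo comparison is the ANCOVA for the primary and secondary endpoints.

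Protocol 2.0 adds a co-intervention in both arms: "In the randomization visit, all participants will receive standard recommendations about lifestyle modifications including healthy" dieting, exercise and weight loss.

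**The concern.** A marker that predicts response to vitamin E must relate to outcome differently on vitamin E than on placebo. A contrast of responders with non-responders does not examine that difference. It shows only which transcripts go with improvement, whatever the cause.

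The documents make improvement without vitamin E plausible. Everyone gets lifestyle advice, and Protocol 6.0 plans to record diet, weight and physical activity. Protocol 1.0 says weight loss and exercise improve NASH in people without HIV, but that their effect in people with HIV is unknown. The extent of placebo improvement is therefore undocumented, and it cannot be assumed to be nil.

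What is at stake is the label. Under the plan's wording, transcripts that pass are described as predicting vitamin E response. Protocol 7.0 looks ahead to larger multicenter trials, and a mislabelled marker could misdirect patient selection there.

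**Working it through.** **The plan's own figures.** The documents give no sample size or power for the signature analysis. Their figures for the primary comparison reproduce with a two-sided two-sample t-test at 25 per group: 91.9% power at effect size 0.97 (stated 91%) and 80.1% at 0.81 (stated 80%). Dropout: 25 / (1 − 0.10) = 27.8, rounded up to 28 per group, as stated. The point below does not depend on these being wrong.

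**The two possible readings of the contrast.**
- Vitamin E participants only: the t-test depends on the association between expression and improvement within that arm. That association may be prognostic (the same on placebo) or specific to vitamin E (absent on placebo), and one arm cannot show which.
- Both arms pooled: placebo participants who improve are classed as responders, so prognostic markers are found more easily because the sample is larger.

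**Illustration.** Inputs from the documents: 28 per arm, threshold p < 0.001, effect size 0.81. Assumptions: the vitamin E effect equals 0.81 SD; the responder cut-off is half of that, 0.405 SD; tissue is available on 14 per arm (half of 28, near the low end if the stated share carries over) or on all 28 (a ceiling).

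Model: improvement Y = 0.81·A + ρ·G + √(1 − ρ²)·e, with A = 1 on vitamin E and 0 on placebo, and G (expression) and e independent standard normal. There is no interaction, so G is prognostic only. A responder has Y > 0.405. The implied response rates are Φ(0.81 − 0.405) = Φ(0.405) = 66% on vitamin E and 1 − 0.66 = 34% on placebo. With equal arms, 34 / (34 + 66) = 34% of pooled responders would be on placebo.

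Share of 4,000 simulated trials in which the prognostic-only transcript passes p < 0.001:

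| Analysis | ρ = 0.3 | ρ = 0.5 | ρ = 0.7 |
|---|---|---|---|
| t-test, vitamin E only, 14 patients | 0.4% | 1.9% | 6.5% |
| t-test, vitamin E only, 28 patients | 1.8% | 9.3% | 37% |
| t-test, pooled, 14 per arm | 1.4% | 7.5% | 30% |
| t-test, pooled, 28 per arm | 4.5% | 30% | 84% |
| Interaction test, 14 per arm | 0.18% | 0.13% | 0.22% |
| Interaction test, 28 per arm | 0.05% | 0.05% | 0.15% |

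A repeat of the 28-patient, ρ = 0.7 case gave up to 39%. The interaction rows amount to 2 to 9 hits in 4,000, against 4 expected at the nominal 0.1%.

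**The reverse case.** Take a transcript that is purely specific to vitamin E: 0.8 SD of improvement per SD of expression on vitamin E and none on placebo. Its correlation with improvement in the vitamin E arm is 0.8 / √(0.8² + 1) = 0.62. The vitamin E-only t-test flags it in 4.0% of trials with 14 patients and 24% with 28. These rates lie between those for the prognostic-only transcript at ρ = 0.5 and ρ = 0.7, so passing the test does not separate the two kinds of marker.

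**Power of the interaction test.** For that same strong interaction at p < 0.001, power is about 6% to 7% with 14 per arm and about 30% with 28 per arm.

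**The case against.** The strongest reply is that this is a side analysis in a pilot. Protocol 2.0 states an efficacy aim and does not mention a signature. The signature is not among the listed endpoints, and the primary and secondary ANCOVAs do use placebo. That is correct, and it limits the weight of the point without removing it.

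The second reply is that the proposed model would seldom settle the question at this size. That also stands: at 6% to 30% power for a strong interaction, a reader should not infer that the placebo arm can give the answer. It can prevent a false claim of specificity more reliably than it can establish a true one.

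Third, other weaknesses may dominate. If all 47,000 probes were detectable, 47,000 × 0.001 = 47 would pass by chance alone, and with 14 patients a prognostic transcript of modest correlation rarely passes. That is fair, but it is a separate limit. Controlling chance hits would not make the contrast specific to vitamin E.

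Two stronger readings are not supported.
- A reader might infer that placebo participants are left out. The text takes tissue from trial participants generally and is silent on which arms enter the test.
- A reader might infer that every hit would be merely prognostic. Hits could be of either kind; the plan has no means of telling which.

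The hepatitis C example gets one sentence in the documents, so no argument is built on it.

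**Conclusion.** The point holds. The stated aim is predictive and specific to vitamin E, while the stated method measures association with improvement from any cause. Nothing elsewhere in either document supplies the missing contrast. This follows from the text and needs no assumed numbers.

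The size does rest on assumptions: the correlation, the responder cut-off, the vitamin E effect and the number with tissue are not given for this analysis. Across the cases shown, a transcript with no vitamin E-specific effect passes the threshold in about 0.4% to 37–39% of trials using vitamin E participants only, and in about 1.4% to 84% if the arms are pooled. The nominal rate is 0.1%, and the interaction test stays near it.

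A reader should not carry this over to the efficacy result. The primary and secondary comparisons, the sample size and participant safety do not depend on this step. It is a correction that should be made to an ancillary analysis.

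**What to change.** - State that any signature derived from responders versus non-responders is exploratory and has not been shown to be specific to vitamin E. This is the realistic minimum.
- State which arms supply tissue, and use the available frozen tissue from both. Protocol 3.0 requires the biopsy before enrollment, so availability of tissue should not depend on arm.
- Model change in MR-PDFF on expression, treatment and expression-by-treatment. Using the continuous change also avoids the undefined term responder; if a responder class is kept, define it.
- Call a transcript or signature predictive of vitamin E response only on the basis of the interaction.

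Cost: a few lines of SAP text and an added model term, plus assay cost if placebo tissue was not already to be run. The downside is the low interaction power shown above: few or no transcripts may be called predictive, and the report should say so in advance.

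### The gene-signature AUC has no stated validation: scored in the patients who chose the transcripts, it would sit at about 0.8 to 1.0 even if no gene predicted response

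*SAP*

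**What the plan says.** The aim is to "identify expression signature that predict response to vitamin E therapy" from pre-treatment liver tissue. SAP, Statistical Considerations, and Protocol 8.0 give the same steps:

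1. Use a chip that "targets more than 47,000 probes derived from the NCBI RefSeq Release 38". Tissue is expected to be "available for expression analysis on a sizable proportion of the subjects (>50%) undergoing liver biopsies".
2. Filter: "After detectable transcripts are identified, expression data will be standardized". The number expected to survive is not given.
3. Compare responders with non-responders by t-test, transcript by transcript: "For this, a significance cut-point of $p < 0.001$ will be used".
4. Apply hierarchical clustering and network and pathway analysis. No rule says how many transcripts go forward.
5. Model: "A logistic multivariate-based analysis will be used to build up a receiver operating characteristic (ROC) curve".
6. Performance: "the area under the ROC curve (AUC) will be calculated to assess the average sensitivity of the biomarker in discriminating the responders and non-responders".

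The documents do not say which patients supply the AUC. They name no hold-out set, resampling, external cohort or false-discovery rate. They do not define a responder, although the primary outcome is a continuous change in MR-PDFF. They do not say whether one arm or both are analysed; the stated aim points to the vitamin E arm without settling it.

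**The concern.** Steps 3 to 6 describe a single path through a single set of patients. A transcript reaches the model because it separated these responders from these non-responders. An AUC in the same patients then measures that separation a second time. With thousands of candidates and a few dozen patients, some transcripts separate the groups well by chance, and the AUC will be high whether or not any gene matters.

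At stake is the claim that a signature exists. A reader shown an AUC above 0.9 would take it as evidence of prediction, when noise alone can produce that value at the likely sample sizes.

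**Working it through.** **The plan's own figure.** The documents give no power or precision figure for the signature. Their only calculation is for the primary t-test with 25 per group. It reproduces (91.9% at effect size 0.97, 80.1% at 0.81) and does not bear on this point.

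**Inputs from the documents.** Threshold 0.001; at most about 47,000 transcripts; at most 56 patients, 28 per arm; tissue expected in more than half of those biopsied.

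**Assumed inputs.** Two-sided tests; 10,000 or 47,000 detectable transcripts; responder splits of 7 v 7, 14 v 14, 8 v 20 and 28 v 28; the model takes the top probe, the top three, or the means of up to three clusters. Correlation at 10,000 transcripts was none, 0.6 in blocks of 100, 0.7 in blocks of 500, or 0.6 in blocks of 1,000. The pathway step could not be modelled.

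**Step 1: false transcripts if nothing predicts response.** Expected number = transcripts × 0.001.
- 10,000 × 0.001 = 10
- 47,000 × 0.001 = 47

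The mean does not depend on correlation, but the typical count does. At 10,000 transcripts the median was 8 to 10 with no or local correlation (0 to 0.5% of runs selected nothing), and 2 to 4 with strong correlation (12 to 33% selected nothing). At 47,000 the median was 30 to 48 and no run was empty.

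**Step 2: why a strict cut does not protect the AUC.** To pass p<0.001, the observed standardised difference must be at least d = t × √(1/n₁ + 1/n₂). For roughly normal data the AUC of that probe is about Φ(d/√2).
- 7 v 7: t = 4.318, d = 4.318 × √(2/7) = 2.31, AUC about 0.95
- 14 v 14: t = 3.707, d = 3.707 × √(2/14) = 1.40, AUC about 0.84
- 28 v 28: t = 3.480, d = 3.480 × √(2/28) = 0.93, AUC about 0.75

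So any probe that passes, true or false, carries at least about this AUC in the patients who selected it. A stricter cut raises that floor.

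**Step 3: the whole path with no signal.** 10,000 transcripts, 200 runs per setting. Median same-patient AUC among runs that selected a probe, ranges over the four correlation structures:

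| Split | Top probe | Top three | Cluster means |
|---|---|---|---|
| 7 v 7 | 1.00 | 1.00 | 1.00 |
| 14 v 14 | 0.88–0.90 | 0.93–0.99 | 0.94–1.00 |
| 8 v 20 | 0.91–0.93 | 0.95–1.00 | 0.96–1.00 |
| 28 v 28 | 0.78–0.80 | 0.82–0.92 | 0.83–0.99 |

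Five-fold cross-validation with selection repeated inside each fold gave mean AUCs of 0.46 to 0.53. With 47,000 transcripts (100 runs per setting) the same-patient ranges were 0.80–1.00, 0.88–1.00 and 0.97–1.00.

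A second set of null simulations scored the model in 400 fresh patients per run. They gave 0.49 to 0.51 there, against same-patient means from 0.77 to 1.00. The 0.77 came from 1,000 transcripts, 56 patients and one probe, with 30% of runs empty.

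**Step 4: can the same-patient AUC tell signal from noise?** 10,000 transcripts, three probes, true effects of 1.5 SD. One such gene has its own AUC of Φ(1.5/√2) = 0.86.

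| Split | Truth | Same-patient AUC | Selection inside folds |
|---|---|---|---|
| 14 v 14 | none | 0.93–0.99 | 0.48–0.49 |
| 14 v 14 | one gene | 0.96–1.00 | 0.53–0.59 |
| 14 v 14 | 50 genes | 0.97–1.00 | 0.77–0.93 |
| 28 v 28 | none | 0.82–0.92 | within 0.46–0.53 |
| 28 v 28 | one gene | 0.91–0.95 | 0.68–0.74 |
| 28 v 28 | 50 genes | 0.93–1.00 | 0.86–0.95 |

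At 7 v 7 the same-patient AUC was 1.00 in all three cases.

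**Step 5: false-discovery reporting.** At 14 v 14 the median Benjamini-Hochberg q-value of the selected probes was 0.76 to 0.84 with no signal and 0.08 to 0.14 with 50 true genes. The q-value therefore carries information that p<0.001 alone does not.

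**The case against.** The strongest reply has four parts.

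- **Same-patient scoring is inferred.** The text does not exclude resampling, and it refers to a wider project (Specific Aim 2) whose documents are not here. This stands as a caveat. Still, no other data set or procedure is named, and an analyst who follows the text would score the model in the same patients.
- **A cut 50 times stricter than 0.05 is a multiplicity guard.** It is, informally: it holds the expected false transcripts to 10 per 10,000. It is not false-discovery or family-wise control, and Step 2 shows that it does nothing for the AUC.
- **The sizes rest on assumptions, and 28 v 28 is unlikely.** True: 28 v 28 needs tissue and outcome from all 56 patients in both arms. At that size the null and signal AUCs overlap much less, so calling the same-patient AUC uninformative fits 7 v 7 and 14 v 14 better. The medians also leave out runs that selected nothing. Even so, the inflation appeared in every setting tried.
- **The stakes are small and cross-validation is weak at this size.** The signature is neither a primary nor a secondary endpoint, and the next trial is to be justified by liver fat and NASH markers. At 7 v 7 the fold-internal AUC was 0.48 to 0.51 with one true gene and 0.57 to 0.65 with 50. This limits the importance of the point and belongs in the report, but it does not make the biased figure preferable.

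The cited hepatitis C precedent plays no part here: it reports accuracy, not AUC, and its validation cannot be seen.

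**Conclusion.** The concern holds. Followed as written, and on the natural reading that selection and scoring use the same patients, the plan yields an AUC of about 0.8 to 1.0 when the true value is 0.5. The exact size depends on the number with tissue, the responder split, the number of detectable transcripts, their correlation and the number of predictors; the documents fix none of these. The direction does not depend on them. The undefined responder and unstated arm are separate gaps that must be closed before the analysis can be run. The harm is confined to this exploratory analysis, so it should be fixed but does not threaten the trial's main comparison.

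**What to change.** 1. Report the AUC only from cross-validation that repeats probe selection, any clustering or pathway reduction, and the logistic fit inside each fold, with a 95% confidence interval. A bootstrap optimism correction of the whole path would serve equally well. If the pathway step needs manual judgement, keep it descriptive and outside the AUC model. State in advance what happens when no probe passes in a fold; a constant prediction and the top-ranked probe differed by at most 0.02 in AUC.
2. Keep p<0.001 as a labelled screen if wished. Report the number of transcripts tested, that number × 0.001, and the q-value of each selected probe.
3. Fix the responder definition and the arm or arms before unblinding. Do not claim prediction of response to vitamin E specifically without a comparison with placebo.
4. Label the analysis hypothesis-generating.

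**Cost.** SAP wording and a little computing; no new samples. The AUC will be lower and imprecise. At a true AUC of 0.7, the Hanley-McNeil variance [A(1−A) + (n₁−1)(Q₁−A²) + (n₂−1)(Q₂−A²)]/(n₁n₂), with Q₁ = A/(2−A) = 0.538 and Q₂ = 2A²/(1+A) = 0.576, gives approximate 95% half-widths of 0.28 at 7 v 7, 0.20 at 14 v 14 and 0.14 at 28 v 28, ignoring dependence between folds. A real but narrow signal can be missed: in an 11 v 11 training fold, the power for one 1.5 SD gene to pass p<0.001 is 0.41.

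Replacing the screen with a 10% Benjamini-Hochberg rule is not proposed. For that lone gene at 14 v 14 the threshold becomes 0.1/10,000 or 0.1/47,000, and power falls from 0.61 to 0.12 or 0.06.
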